4. CHANGES IN THE PLANNED ANALYSIS OF THE STUDY

All analyses described in the TSAP are outlined in the CTP. The following changes compared to the protocol will be made:

According to the Reference Document 3 of the Boehringer Ingelheim (BI) Statistical Position Paper on Statistical Methods for PK (14), the 90% confidence intervals (CI) should be considered for the assessment of dose proportionality. Therefore, the 90% CI will be used instead of the 95% CI.

The trial was prematurely discontinued on 21 March 2019 after completion of dose group 6 (200 mg) of the SRD part, and without starting the originally-planned BA part of this trial. The TSAP will therefore only describe the analysis of the SRD part.

All subjects up to and including the 200 mg dose group have completed their follow-up period. The maximum exposure (C_{max}) observed in the SRD part following doses of 200 mg BI 730460 was 1,864 nM (gMean). Administration of the originally planned next 2-fold higher dose of 400 mg was not possible due to a higher predicted estimated C_{max} of 3,728 nM which is above the allowed exposure limit of 2,900 nM. Therefore, the SRD part was stopped as with the next planned dose group (400 mg) the pre-defined stopping rule was met. Due to the above mentioned exposure limitation, BI also decided to stop the BA part of trial 1416-0001.

5. ENDPOINTS

5.1 PRIMARY ENDPOINT

Section 5.2.1 of the CTP:

Primary endpoint to assess safety and tolerability of BI 730460 is the number [N (%)] of subjects with drug-related adverse events.

5.2 SECONDARY ENDPOINTS

5.2.1 Key secondary endpoints

This section is not applicable as no key secondary endpoints have been defined in the CTP.

5.2.2 Secondary endpoints

Section 5.5.1.1 of the CTP:

- *AUC_{0-∞} (area under the concentration-time curve of the analyte in plasma over the time interval from 0 extrapolated to infinity)*
- *C_{max} (maximum measured concentration of the analyte in plasma)*

6. GENERAL ANALYSIS DEFINITIONS

6.1 TREATMENTS

It was planned that in total 84 volunteers participate in this study. 72 healthy male subjects will enter the SRD part, according to 9 sequential dose groups comprising 8 subjects per dose group (6 on active and 2 on placebo) and 12 healthy males will enter the BA part (one dose group, all on active).

For details of dosage and formulation see Tables [6.1: 1](#), and [6.1: 2](#) below.

Table 6.1: 1 Labels for treatments for use in the CTR (SRD part)

Dose group	Treatment		Short label
1-6	N*	Placebo film-coated tablet	Placebo
1	A	2mg BI 730460 film-coated tablet	BI 2mg
2	B	8mg BI 730460 film-coated tablet	BI 8mg
3	C	25mg BI 730460 film-coated tablet	BI 25mg
4	D	50mg BI 730460 film-coated tablet	BI 50mg
5	E	100mg BI 730460 film-coated tablet	BI 100mg
6	F	200mg BI 730460, film-coated tablet	BI 200mg
7	G**	400mg BI 730460 film-coated tablet	BI 400mg
8	H**	600mg BI 730460 film-coated tablet	BI 600mg
9	I**	800mg BI 730460 film-coated tablet	BI 800mg

*: The placebo group in the safety evaluation will consist of all placebo treated subjects, regardless of the dose group in which they were treated.

** : These dose groups were cancelled.

Dose escalation was stopped after the 200mg dose group, as the results of the preliminary PK analysis indicate that C_{max} for 400 mg (dose group 7) will very likely exceed the CTP stopping criterion. Therefore, all analyses will be performed for the first six dose groups only.

Table 6.1: 2 Labels for treatments for use in the CTR (BA part)

Treatment		Short label
S	50mg BI 730460 film-coated tablet, fasted	BI 50mg fast
U	50 mg BI 730460 film-coated tablet, fed	BI 50mg fed

The trial was stopped after the 200 mg dose group, skipping also the BA part.

The following separate study phases will be defined for the analyses of AEs:

- **Screening** (ranging from 0:00h on day of informed consent until administration time of study drug (BI or Placebo))
- **On treatment**
 - **BI/Placebo treatment** (separately for each treatment, ranging from the time of administration of BI 730460 or Placebo until 0:00h on the day after trial termination date (whatever occurs first))

Please note that all AEs reported between start of trial drug administration and the trial termination date will be considered on treatment (i.e. no follow-up period is considered in this trial).

Two types of AE displays will be provided in the report:

A) Section 15.3 and Appendix 16.1.13.1.8 (for ClinicalTrials.gov and EudraCT) of the CTR displays:

In these displays, the on treatment phase will be analysed (labelled with the name of the study treatment (short label)). Screening will not be included in this analysis.

The following totals will be provided in addition:

- a total over all BI treated phases ("**BI Total**")
 - a total over all on treatment phases included in this analysis ("**Total on treatment**") (Section 15.3 only)
- B)** Section 15.4 and Appendix 16.1.13.1.8 (except for ClinicalTrials.gov and EudraCT) of the CTR displays:
- Screening
 - On treatment (labelled with the name of the study treatment (short label))

In Section 16.1.13.1.8 AE tables, the following totals will be provided in addition:

- a total over all BI treated phases ("**BI Total**")
- a total over all study phases ("**Total**")

Tables of vital signs, ECG and laboratory values will present results by the above mentioned on treatment phase.

For detailed information on the handling of the treatments refer to Technical TSAP ADS (analysis data set) plan and Analysis Data Reviewer's guide.

6.2 IMPORTANT PROTOCOL DEVIATIONS

Data discrepancies and deviations from the CTP will be identified for all treated subjects.

Consistency check listings (for identification of deviations of time windows) and a list of protocol deviations (e.g. deviations in drug administration, in blood sampling times, etc.) will be provided to be discussed at the Report Planning Meeting and database lock meeting (RPM/DBLM). At this meeting, all manual deviations identified at the sites by the CRAs and deviations too complex to program will be reviewed by the trial team to decide which are considered important. For definition of important protocol deviations (iPD), and for the process of identification of these, refer to the Boehringer Ingelheim (BI) SOP "Identify and Manage Important Protocol Deviations (iPD)" (2).

If any iPDs are identified, they are to be summarised into categories and will be captured in the RPM/DBLM minutes via an accompanying Excel spreadsheet (3). [The following table](#) contains the categories which are considered to be iPDs in this trial. If the data show other iPDs, this table will be supplemented accordingly by the time of the RPM/DBLM at the latest.

The iPDs will be summarised and listed.

Table 6.2: 1 Important protocol deviations

Category /Code	Description
A	Entrance criteria not met
A1	Inclusion criteria violated
A2	Exclusion criteria violated
B	Informed consent
B1	Informed consent not available
B2	Informed consent too late
C	Trial medication and randomisation
C1	Incorrect trial medication taken
C2	Randomisation not followed
C3	Non-compliance
C4	Incorrect intake of trial medication
C5	Improper washout between treatments
D	Concomitant medication
D1	Concomitant medication with the potential to affect the assessment of the trial medication
E	Missing data
E1	Certain violations of procedures used to measure secondary data
F	Incorrect timing¹
F1	Certain deviations from time schedule used to measure secondary data
G	Other trial specific important deviations
G1	Appropriate fasting condition not met
G2	Other protocol deviations affecting safety and rights

¹ Time deviations will only be flagged as iPD, when leading to exclusion of the entire subject from an analysis set

6.3 SUBJECT SETS ANALYSED

- Treated set (TS):
This subject set includes all subjects who were dispensed study medication and were documented to have taken at least one dose of investigational treatment.
This is the full analysis set population in the sense of ICH-E9 (1). It is used for demographics, baseline characteristics, and safety analyses.
The ECG analyses are performed on the TS, except for the exposure-response analyses, which are performed on the ECGPCS defined below.

Section 7.3.2 of the CTP: *Pharmacokinetic parameters of a subject will be included in the analysis unless the subject has an important protocol deviation relevant for the evaluation. Whether a protocol deviation is important will be decided no later than in the Report Planning Meeting.*

Reasons for exclusion of single pharmacokinetic parameters may be:

- *The subject experiences emesis at or before two times median tmax. Median tmax is to be determined for the test product excluding the subjects experiencing emesis.*
 - *The subject experiences emesis at any time during the labelled dosing interval.*
 - *Time deviations*
 - *Use of restricted medications*
- PK analysis set (PKS):
The PK analysis set (PKS) includes all subjects from the TS receiving BI 730460 who provide at least one secondary PK parameter that was not excluded according to the description above.
It is used for assessment of dose proportionality and the descriptive analyses of PK parameters.

The descriptive analysis of PK concentrations will be based on the ADS ADPC.

- ECG Pharmacokinetic Concentration Set (ECGPCS):
This subject set includes all subjects from the TS for whom at least one pair of a valid drug plasma concentration of BI 730460 and a corresponding (i.e. time-matched) ECG endpoint to be used in the exposure-response analyses was provided. For placebo subjects, the plasma concentration is set to zero and hence always considered as valid.
The decision whether a time deviation between PK blood sampling and ECG recording is acceptable (and thus whether the pair of values will be used) is to be made no later than at the DBLM/RPM before database lock.

Table 6.3: 1 Analysis sets for endpoints/data description

Endpoint/data description	Analysis set		
	TS	PKS	ECGPCS
Primary and further safety endpoints (incl. ECG)	X		
ECG endpoints and plasma concentrations used in exposure-response analysis			X
Secondary PK endpoints		X	
Demographic/baseline data	X		
Important protocol deviations	X		
Disposition	X		

6.5 POOLING OF CENTRES

This section is not applicable, because the study was performed in only one centre.

6.6 HANDLING OF MISSING DATA AND OUTLIERS

Handling of missing data and outliers will be performed as described in the CTP, Section 7.4.

The only exceptions where imputation might be necessary for safety evaluation are AE dates. Missing or incomplete AE dates are imputed according to BI standards (see 001-MCG-156_RD-01 (4)).

Missing data and outliers of PK data are handled according to BI standards (see 001-MCS-36-472_RD-01) (5).

If single cardiac cycles of an ECG (out of the generally four) are missing, the arithmetic mean for this single ECG will be computed with the reduced (1, 2 or 3) number of cardiac cycles.

If replicate ECG recordings are missing, the arithmetic means per time point will be computed with the reduced number (1 or 2) of recordings.

For the classification of the on treatment QTc/QT intervals into “no new onset” / “new onset” categories, a missing value is obtained only in case that

- (i) all on treatment values are missing and
- (ii) the baseline value is less than or equal to 500 msec, or missing.

If condition (i) is fulfilled but the baseline value is greater than 500 msec, this case will be categorized as ‘no new onset’. If baseline is missing and the maximum on treatment QTc interval is greater than 450 msec (or 500 msec for QT interval, respectively), this is classified as a ‘new onset’ in the respective category. If baseline is missing and the maximum QTc interval is less than or equal to 450 msec (or 500 msec for QT interval, respectively), this will be categorized as ‘no new onset’. If baseline is missing, a QTc/QT interval > 500 msec at any time on treatment will be a notable finding.

For placebo subjects, the missing plasma concentration values will be replaced by 0 for the exposure-response analyses. For subjects on active drug, missing plasma concentration values with ‘BLQ’ in the comment field will be replaced by ½ LLOQ.

6.7 BASELINE, TIME WINDOWS AND CALCULATED VISITS

The baseline value is defined as the last measurement before administration of BI 730460 or Placebo.

Section 6.1 of the CTP: *Exact times of measurements outside the permitted time windows will be documented. The acceptable time windows for screening and end of trial examination are given in the CTP Flow Chart.*

Study measurements and assessments scheduled to occur ‘before’ trial medication administration on Day 1 are to be performed and completed within a 3 h-period prior to the trial drug administration (including blank values for PK

Starting from 72 h post administration a deviation from the scheduled time for PK sampling of ±70 min is acceptable.

The acceptable deviation from the scheduled time for vital signs, ECG and laboratory tests will be ± 15 min for the first 6 h after trial drug administration and ± 30 min thereafter. Starting from 72 h post administration a deviation from the scheduled time for vital signs, ECG and laboratory tests of ±70 min is acceptable.

Adherence to time windows will be checked via the consistency check listings at the RPM/DBLM.

Unscheduled measurements of laboratory data or vital signs will be assumed to be repeat measurements of the most recent scheduled measurement (e.g. for follow-up or confirmation

of a particular value). Therefore, unscheduled measurements will be assigned to the planned time point of the previous scheduled measurement.

There will be a centralised evaluation of the 12-lead ECG recordings at the time points and for the ECG recordings specified in the Table 6.7: 1 below:

Table 6.7: 1 Time schedule of 12-lead ECG recordings (SRD part)

Visit	Day	Planned time [hh:mm] (relative to drug administration)	Study phase	Central evaluation
1	-21 to -1		Screening	NA
2	1	-1:30	Predose	first of three replicate ECG
		-1:15	Predose	first of three replicate ECG
		-1:00	Predose	first of three replicate ECG
		0:30	On treatment	first of three replicate ECG
		1:00		first of three replicate ECG
		2:00		first of three replicate ECG
		3:00		first of three replicate ECG
		4:00		first of three replicate ECG
		6:00		first of three replicate ECG
		8:00		first of three replicate ECG
		10:00		first of three replicate ECG
		12:00		first of three replicate ECG
		2		24:00
	34:00		first of three replicate ECG	
3	48:00	first of three replicate ECG		
3	9 to 13		End of trial examination	NA

At Visits 1 and 3, single ECGs will be recorded.

At Visit 2, triple ECGs will be recorded (three single ECGs within 180 sec).

Prior to study drug administration, 3 triplicate ECGs (9 single ECGs) will be recorded. The vendor will analyse the first single ECG per triplicate for all on treatment timepoints.

The baseline value of an ECG variable is defined as the mean of the first triplicate ECG measurement at -01:30 prior to drug administration.

Section 5.2.4.1 of the CTP: *For the SRD part, central ECG lab evaluation will be performed post-study for the first of three replicate ECGs per time point on Days 1, 2 and 3. For baseline, where 3 triplicate ECGs are recorded, only the first triplicate ECG (i.e. 3 single ECGs) will be evaluated. This will include the determination of cardiac QRS-axis as assessed by the ECG machine's algorithm as well as the intervals RR, PR, QRS and QT measured*

semi-automatically. The remaining second and third replicate ECG will be stored for additional analysis if required, e.g. by authorities at a later time point.

For the exposure response analyses, pairs of ECG variables and corresponding plasma concentrations will be built using the same planned time points, e.g. HR change from baseline and the plasma concentration measured at planned time 1:00 will build one pair. Whether a time deviation between PK blood sampling time and corresponding ECG recording is too big and the pair has to be excluded from the analysis will be decided no later than at the RPM. This critical time deviation depends on the PK properties. When plasma concentrations are expected to change only little around a given time point, the acceptable time deviation between ECG recording and PK blood sampling may be bigger.

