2. The time is approximate; the respective procedure is to be performed and completed within 3 h prior to drug administration. Allocation to treatment may be performed at any time following enrolment but must be completed prior to (first) drug administration.
3. If several actions are indicated at the same time point, the intake of meals will be the last action.
4. End of trial examination includes physical examination, vital signs, ECG, safety laboratory, recording of AEs and concomitant therapies.
5. Only urine drug screening and alcohol breath test will be done at this time point.
6. AEs and concomitant therapies will be recorded throughout the trial, but will be specifically asked for at the time points indicated in the Flow Chart above.

7. Safety laboratory to be taken and to be medically evaluated within 3 days prior to administration of study drug; this ambulatory visit including the safety laboratory can be omitted, if the screening examination is performed on Days -3, -2 or -1.
  8. Two blood sample for stability testing will be taken at this time point (refer to Section [5.5.2.4](#))
  9. The ECG recording has to be performed as triplicate at this time point
  10. Sampling times and periods may be adapted based on information obtained during the trial (e.g. preliminary PK data) including addition of samples and visits as long as the total blood volume taken does not exceed 500 mL per subject
- 
13. Two blood samples should be collected: 4.3 mL in sodium citrate tubes and 4.5 mL in lithium heparin tubes.
  14. The ECG will be recorded as single ECG at this time point
  15. At baseline (i.e. Day 1, prior to drug administration) 3 triplicate ECGs are recorded within approximately one hour. The recordings of each first triplicate ECG should be separated by at least 15 minutes.
  16. Only haematology with automatic WBC differential (refer to Table [5.2.3: 1](#)) at this time point.

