### **7.3.3 Safety analyses**

Safety analyses will be performed in accordance with BI standards.

All treated subjects (that is, all subjects who received at least one dose of study drug), will be included in the safety evaluation. Safety analyses will be descriptive in nature and will be based on BI standards.

Treatments will be compared in a descriptive way. The placebo control group in the safety evaluation will consist of all placebo treated subjects, regardless of the dose group in which they were treated. The active treatment groups will be compared to the placebo group in a descriptive way. Tabulations of frequencies/proportions will be used for the evaluation of categorical (qualitative) data, and tabulations of descriptive statistics will be used to analyse continuous (quantitative) data.

The analyses will be done by 'treatment at onset'.

Measurements (such as ECG, vital signs, or laboratory parameters) or AEs will be assigned to treatments (see Section 4.1) based on the actual treatment at the planned time of the measurement or on the recorded time of AE onset (concept of treatment emergent AEs). Therefore, measurements planned or AEs recorded prior to first intake of trial medication will be assigned to 'screening', those between first trial medication intake until the end of trial visit will be assigned to the treatment period, and those after the end of trial examination will be assigned to 'post-study'. These assignments including the corresponding time intervals will be defined in detail in the TSAP.

Additionally, further treatment intervals (analysing treatments) may be defined in order to provide summary statistics for time intervals, such as combined treatments, on-treatment totals or periods without treatment effects (such as screening and post-study intervals).

Adverse events will be coded using the Medical Dictionary for Regulatory Activities (MedDRA). Frequency, severity and causal relationship of AEs will be tabulated by treatment, system organ class and preferred term. SAEs, AESIs (see Section 5.2.2.1) and other significant AEs (according to ICH E3) will be listed separately.

Laboratory data will be compared to their reference ranges. Values outside the reference range as well as values defined as clinically relevant will be highlighted in the listings. Additionally, differences from baseline will be evaluated.

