7.8.2 Laboratory data

The analyses of laboratory data will be descriptive in nature and will be based on BI standards [001-MCG-157] (11).

Laboratory data will be analysed qualitatively via comparison of laboratory data to their reference ranges. Values outside the reference range as well as values defined as possible clinically significant will be flagged in the data listings.

It is the investigator's responsibility to decide whether a lab value is clinically significant abnormal or not (at the RPM/DBLM at the latest).

Descriptive statistics of laboratory data will be calculated by planned time point based on the worst value of the subject at that planned time point (or assigned to that planned time point).

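### SAP 6.7 files an unscheduled laboratory value taken between dosing and the 4 h sample under a pre-dose planned time, so it enters the pre-dose summary row and may leave the on-treatment tables.

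*SAP*

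**What the plan says.** - **Unscheduled values.** SAP 6.7 regards unscheduled laboratory and vital-sign values as repeats of the latest scheduled one, so "unscheduled measurements will be assigned to the planned time point of the previous scheduled measurement". Dosing is not mentioned as a boundary.
- **Laboratory summaries.** SAP 7.8.2 has descriptive statistics "calculated by planned time point based on the worst value of the subject at that planned time point", and includes values assigned to that time. SAP 7.8.3 does the same for vital signs, but with the last value instead of the worst.
- **Phase.** Protocol 7.3.3 assigns measurements "based on the actual treatment at the planned time of the measurement". It adds that "measurements planned or AEs recorded prior to first intake of trial medication will be assigned to" screening. The details are left to the SAP.
- **Tables.** SAP 6.1 states: "Tables of vital signs, ECG and laboratory values will present results by the above mentioned on treatment phase". The phases it refers to start and end at the time of administration, but they are introduced for adverse events.
- **Schedule.** In the SRD flow chart the last routine laboratory before dosing falls on Day -3 to -1: "Safety laboratory to be taken and to be medically evaluated within 3 days prior to administration of study drug". That visit may be skipped if screening itself falls on those days. Of the Day 1 entry at -2:00 the flow chart says: "Only urine drug screening and alcohol breath test will be done at this time point". The first post-dose safety laboratory is at 4:00, and protocol 5.2.3 also refers to a 4-hour sample.

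**The concern.** The repeat convention works when both values lie on the same side of dosing. It fails when the previous scheduled value is pre-dose and the unscheduled one is post-dose, because a value that could show an acute drug effect is then filed with the untreated values.

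The hours concerned matter. Protocol 2.3 describes the first 4 hours as the expected time of highest exposure, and protocol 1.2.5 gives a tmax of about 2 to 3 hours for a similar compound. Safety is the primary objective of the SRD part, and each dose group has only 6 actively treated subjects, so a single value can visibly change a row. Protocol 5.2.2.1 itself foresees unscheduled blood tests when symptoms suggest hepatic injury.

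**Working it through.** The plan has no figure to reproduce. The check applies the written rules in order to the SRD laboratory schedule.

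**Inputs**
- Scheduled safety laboratory (SRD flow chart): screening, -72 h (nominal, Day -3 to -1), 4 h, 24 h, 72 h, 168 h (haematology only), end of trial.
- Rule 1 (SAP 6.7): planned time of an unscheduled sample = planned time of the latest scheduled sample before it.
- Rule 2 (protocol 7.3.3): phase = screening if the planned time is before dosing, otherwise on treatment.
- Rule 3 (SAP 7.8.2): value in a row = worst value at, or assigned to, that planned time.

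**Rules 1 and 2 applied**

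| Actual time of unscheduled sample | Planned time assigned | Phase by planned time | Phase by actual time |
|---|---|---|---|
| 0.5 h | -72 h | screening | on treatment |
| 1 h | -72 h | screening | on treatment |
| 2 h | -72 h | screening | on treatment |
| 3 h | -72 h | screening | on treatment |
| 3.9 h | -72 h | screening | on treatment |
| 4.5 h | 4 h | on treatment | on treatment |
| 23 h | 4 h | on treatment | on treatment |
| 30 h | 24 h | on treatment | on treatment |

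If the -72 h visit is omitted, the first five rows go to the screening sample and the phases are the same. Counting the -2:00 entry as the previous measurement would not help either, since it too is pre-dose. The affected window is 4 h - 0 h = 4 h. Outside it the rule gives no phase error.

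**Rule 3 applied.** The pre-dose row shows the worse of the true pre-dose value and the post-dose value. A worse post-dose value therefore displaces the pre-dose one.

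**Does the other phase definition remove the problem?** Suppose the dosing-time boundary in SAP 6.1 also governs laboratory data. A 2 h sample is then on treatment by phase but still carries planned time -72 h. Because SAP 7.8.2 summarises by planned time, it still has no correct post-dose row. The planned-time error thus holds under either definition. Only the screening label depends on which one applies.

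**Vital signs.** Rule 1 is the same, and under SAP 7.8.3 the last value assigned to the pre-dose time is used, so a post-dose reading would displace the pre-dose one. The window runs from dosing to the first scheduled post-dose reading. The flow-chart columns are shifted in the extracted text, so its length is not claimed here. If the last mark in the 0:30 row is vital signs, it is 30 minutes.

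**Comparison with ECGs.** Protocol 5.2.4.1 also assigns unscheduled safety ECGs to the prior scheduled time, but keeps them out of the statistics on interval lengths. Laboratory and vital-sign values have no such safeguard.

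**The case against.** The strongest reply is that little is lost.

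- **Adverse events.** Changes judged clinically relevant are adverse events (protocol 5.2.2.1) and are placed by recorded onset, so they stay on treatment and in the primary endpoint. This stands.
- **Listings.** All individual values are listed (SAP 7), and out-of-range or possibly clinically significant laboratory values are flagged (SAP 7.8.2). This stands.
- **Baseline.** A reader might infer that a worse pre-dose row makes later values look like no change or recovery. SAP 6.7 defines baseline as the final value before dosing. Read by actual time, a post-dose sample cannot become baseline, so changes from baseline need not shift. Only the raw pre-dose row is exposed.
- **The screening label.** A reader might infer that these values are certain to leave the on-treatment tables. The documents do not settle this. Protocol 7.3.3 points there but defers to the SAP, whose dosing-time boundary is stated for adverse events. SAP 6.1 also refers to a technical dataset plan that is not among the documents and could use actual time.
- **Contradictory tables.** A reader might infer that laboratory and adverse event tables would contradict each other. They measure different things, so a mismatch is possible but does not follow.
- **Size.** One subject in 6 is 1/6 = 16.7% of a dose group. That is the weight of one subject, not an estimate of how often this happens. The documents do not show that any such sample was taken.

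The repeat convention is deliberate, meant for follow-up or confirmation of a value. That supports it within one side of dosing, not across it.

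**Conclusion.** The point holds in limited form and should be corrected. As written, SAP 6.7 gives every unscheduled SRD laboratory sample from the 4 hours between dosing and the first scheduled post-dose sample a pre-dose planned time, and SAP 7.8.2 then summarises it in the pre-dose row. Loss from the on-treatment laboratory tables is possible under protocol 7.3.3 but not certain. The vital-sign version is real, with a window left open.

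The damage is confined to descriptive summaries, chiefly abnormal values not reported as adverse events. The number of such samples is unknown, probably small and possibly zero. The SAP was written after all subjects up to 200 mg had completed follow-up, so it concerns a closed data set of six dose groups.

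The conclusion assumes that the rules are programmed as written and that baseline is derived from actual times. If the dataset plan already uses actual times, the SAP text should say so.

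**What to change.** Add to SAP 6.7:

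1. A laboratory or vital-sign value obtained after dosing is never assigned to a pre-dose planned time.
2. Study phase for these values follows the actual date and time relative to dosing.
3. A post-dose value taken before the first scheduled post-dose measurement is shown as unscheduled, on treatment.

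Such a value should not be moved forward to the next planned time. Under the worst-value rule, a 0.5 h sample moved to 4 h could displace the true 4 h value.

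Record this in SAP Section 4 as a change to protocol 7.3.3. The cost is a short SAP addition and one derivation in the analysis datasets. No new data are needed, and no trial procedure changes. Counting the unscheduled values whose actual time lies between dosing and the first scheduled post-dose measurement would show whether any table changes.
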